2.4.3.3 Impact of the Biology of the Human Acellular Vessel on Patency

The HAV is a unique biological product - it is not a synthetic graft; it has inherent biological properties that Humacyte believes may significantly differentiate it from synthetic grafts. Furthermore, Humacyte believes that those differences are more likely to manifest themselves in the longer term, when remodeling has progressed and host cells have populated the matrix. It is of interest that in a single anecdotal case, there is evidence of 'healing' of cannulation tracts with host cell infiltration into cannulation sites.

The HAV is cultured from adult human aortic vascular smooth muscle cells, in a bioreactor that imparts arterial-like strain conditions on the growing cells. After an 8-week culture period, the tissue is decellularized, to produce the final HAV. The HAV is comprised of the ECM proteins that are secreted by the vascular smooth muscle cells during culture. These proteins include collagen types I and III, but also the glycoproteins and proteoglycans that are typically found in normal human arteries.

When host cells populate the HAV after implantation, they encounter these vascular ECM proteins. It is possible that the responses of these populating cells in the HAV may be different from the responses of host cells that infiltrate PTFE grafts. Pre-clinical work in primates ([Dahl 2011](#)) and in pigs ([Quint 2011](#)) showed that the propensity for intimal hyperplasia in decellularized HAVs was less than is typically seen in vein and PTFE grafts in pigs and baboons, respectively.

These pre-clinical studies point to a potential for the HAV to develop less intimal hyperplasia than synthetic vascular grafts. This is an important consideration since intimal hyperplasia is a common cause of graft failure and abandonment. Early data from the ongoing Phase 2 trials support the potential for longer conduit survival. The observed Secondary Patency with HAV appears to be superior to that seen in historical trials with PTFE grafts; 89% at 1 year vs 50% to 60% for synthetic grafts.

2.4.3.4 Choice of Secondary Patency as the Primary Endpoint

For the reasons described above, the study's analysis strategy is designed to examine those aspects of efficacy that primarily would be driven by the inherent biological aspects of the HAV. For these reasons, the primary objective of the study is the comparison between treatment groups of Secondary Patency, with Primary Patency as a key secondary objective.

A further consideration for selecting Secondary Patency as the primary efficacy endpoint (compared with the often use of Primary Patency) is that this is a randomized and controlled study. In this setting, the impact of physician decisions on interventions will be balanced across the two arms (not the case in historical studies which were typically single-arm assessments of

conduit performance). The prospective development by the Clinical Events Committee of clinical guidelines on management decisions will encourage physician balanced decisions about interventions to maintain patency across the two arms of the study (see [2.4.3.5](#) below).

2.4.3.5 Controlling against Bias

This is an open-label, comparative study. It is not possible to blind the investigators or study subjects. Study endpoints (see [Section 4.2](#)) will be determined by the clinical decisions of the investigators (except as noted below for study conduit revisions and access-related infections). To reduce the potential for bias the Clinical Events Committee (CEC) (as described in [Section 9.6.2](#)) will:

- Prospectively provide to study sites a set of clinical guidelines for study conduit interventions and abandonment.
- Review study conduit interventions and abandonment in a blinded fashion to assess compliance with these guidelines.
 - Assessments by the CEC of the appropriateness of interventions will be provided to the DMC by the CEC Coordinator (an employee of the CRO with no other study-related responsibilities). As part of their oversight of study conduct, the DMC will review the pattern of interventions and abandonments between treatment groups overall and by study site to assess whether the management of access complications is similar in the two treatment groups.
- Adjudicate study conduit revisions to determine whether the original study conduit was still being used for dialysis.
- Adjudicate access-related infections using the Centers for Disease Control and Prevention (CDC) definitions for dialysis-associated infections ([CDC 2013](#)).

The outcome of these adjudications (i.e., those involving study conduit revisions and access-related infections) will be used as endpoints in the trial rather than the investigator determinations. All other study endpoints will be based on the clinical decisions of the investigators.

Additionally, across-study cumulative event rates overall and by study arm will not be available to staff involved in the management of the study or study subject care.

2.5 Potential Risks and Benefits

2.5.1 Potential Risks

It is anticipated that subjects participating in the study will be exposed to the same risks as those associated with AV graft implantation (some of which have been reported in Phase 2 trial with the HAV – see Investigator Brochure). Risks associated with the HAV and the ePTFE graft may include, but are not limited to, the following:

- Aneurysm or pseudo-aneurysm formation
- Conduit rupture
- Bleeding and hematoma formation at the surgical site or the dialysis puncture sites
- Thrombosis/occlusion of the conduit or host vessels
- Stenosis of the conduit or its anastomoses
- Infection of the conduit, at the surgical site or a systemic infection
- Skin erosion
- Steal syndrome and/or high output cardiac failure
- Swelling of the limb

The risks anticipated in this study are similar to those associated with currently marketed prosthetic grafts used for dialysis access. There was one aneurysmal dilatation of the HAV reported in the Phase 2 experience. The superficial site of implantation of the conduit facilitates clinical and regular ultrasound monitoring, allowing any such complication to be recognized and treated promptly, and thus minimizing potential risk to the subject.

The HAV is grown using donor human aortic smooth muscle cells. The HAV is decellularized during manufacturing and thus consists of only human ECM proteins. It is possible that the HAV may provoke an immune response which may lead to damage of the HAV and possible cross reactivity against host proteins. Antibody formation will be assessed by monitoring of PRA levels.

2.5.2 Potential Benefits

Subjects who undergo implantation of the Humacyte HAV may benefit from reduced infections and improved patency, which may translate into a reduced number of interventions versus a conventional ePTFE graft. Based on the known biology of the HAV, the HAV has the potential to offer a reduced risk of infection and less intimal hyperplasia, which could offer a longer period of use (i.e., delayed abandonment).

3. STUDY OBJECTIVES

3.1 Primary Objective

To compare the Secondary Patency of the HAV with that of the ePTFE graft when used as a conduit for hemodialysis.

3.2 Secondary Objectives

3.2.1 Key Secondary Objectives:

Efficacy

To compare the Primary Patency of the HAV with that of the ePTFE graft.

Safety

To compare the rate of access-related infections for the HAV with that of the ePTFE graft.

3.2.2 Other Secondary Objectives:

Efficacy

1. To compare the rate of interventions needed to maintain/restore patency of the HAV with that of the ePTFE graft.
2. To compare the Primary Assisted Patency of the HAV with that of the ePTFE graft.
3. To describe the histopathological remodeling of samples from HAV and ePTFE grafts.
4. To compare the efficiency of dialysis with the HAV with that of the ePTFE graft in a subset of subjects.

Safety

1. To compare the safety and tolerability of the HAV with that of the ePTFE.
2. To compare the relative rates of true aneurysm and pseudo-aneurysm formation.

4. STUDY DESIGN

4.1 Description of the Study Design

This is a Phase 3, prospective, multicenter, multinational, open-label, randomized, two-arm, comparative study. Subjects who sign informed consent would undergo study-specific screening assessments within 35 days from the day of informed consent.

On the day of surgery (Day 0), subjects could still be undergoing screening assessments, such as confirmation of inclusion/exclusion criteria, to determine their eligibility before they are randomized in the study. Eligible study subjects will be randomized to receive either a HAV or one of two commercially available ePTFE grafts and followed to 24 months post-implantation at routine study visits regardless of patency status. After 24 months, subjects with a patent study conduit will be followed (while the study conduit remains patent) for up to 5 years (60 months) post-implantation at routine study visits.

4.2 Study Endpoints

4.2.1 Primary Endpoint

Time to loss of Secondary Patency from implantation

- Defined as 'the interval from the time of access placement until access abandonment', i.e., patent with or without interventions ([Sidawy 2002](#)).
- "Abandonment" defined as no remaining segment of the study conduit is incorporated into the vascular access circuit used for dialysis (conversely, if some portion of the study conduit is still being used for dialysis it is not considered abandoned).

4.2.2 Secondary Endpoints

4.2.2.1 Key Secondary Endpoints:

Efficacy

Time to loss of Primary Patency from implantation

- Defined as 'the interval from the time of access placement until any intervention designed to maintain or reestablish patency, access thrombosis or the measurement of patency', i.e., patent without interventions ([Sidawy 2002](#)).

Safety

Access-related infections ([CDC 2013](#))

4.2.2.2 Other Secondary Endpoints:

Efficacy

1. Rate of interventions required to achieve/maintain Secondary Patency
2. Time to loss of Primary Assisted Patency from implantation
 - a. Defined as 'the interval from the time of access placement until access thrombosis or the time of measurement of patency, including intervening manipulations (surgical or endovascular interventions) designed to maintain the functionality of patent access' i.e., patent without an intervention to clear a thrombus ([Sidawy 2002](#)).
3. Histopathological remodeling of any study conduit (based on any samples collected).
4. The efficiency of dialysis as assessed by $spKt/V_{urea}$ (obtained from dialysis unit for a subset of subjects).

Safety

1. Frequency and severity of AEs
2. Study conduit dilatation:
 - a. True aneurysm formation (conduit lumen diameter > 9 mm)
 - b. Pseudo-aneurysm formation
3. Study conduit spontaneous rupture
4. Anastomotic bleeding or spontaneous rupture

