2.4.3.2 Drivers of Graft Failure

The natural history of an implanted dialysis graft is not well described; it is likely that the causes of graft failure vary over the time from graft placement – though in all cases the final failure is thrombosis:

1. Very early failures are likely related to surgical technique leading to thrombosis (e.g., twisting of the implant), immediate failure (e.g., dehiscence at an anastomosis), or thrombosis occurring because of inherent thrombogenicity of the graft material.
2. Later thromboses are most likely related to a stenosis, either within the graft itself or, more often, associated with the development of intimal hyperplasia either at the venous anastomosis, where high blood flow creates zones of high shear stress, or in the proximal vein.
3. Other factors contributing to the development of later thromboses include repeated graft punctures needed to achieve dialysis, with the associated blood flow turbulence and mechanical graft damage and pseudoaneurysms.
4. There are also non-graft related causes including post-dialysis hypotension, compression of the access following decannulation, and others usually associated with problems in the draining venous system (e.g., stenosis).
5. Other factors that may cause graft failure are infections and inappropriate dilatation.

Support for these differential drivers of thrombosis comes from a recently published study that compared the patency of standard PTFE grafts with Propaten grafts (heparin bonded) ([Shemesh 2015](#)). In that study, time to first thrombosis (loss of Primary Patency) was superior for Propaten early (up to 6 months), but not later (12 months) suggesting that the bonded heparin was able to reduce early thromboses that were likely unrelated to the inherent properties of the graft material, but that heparin did not offer benefit when thromboses were more likely to be related to stenoses (intimal hyperplasia). However, in two recent retrospective studies comparing non-heparin bound ePTFE grafts to heparin bound ePTFE grafts, neither

Allemang, nor Zea revealed improvement in patency with heparin bound grafts in the dialysis access clinical setting (Allemang 2014, Zea 2016).

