4.2.3 Events of Special Interest

Events of Special Interest related to interventions and infections will be evaluated and include the following:

- Study conduit abandonment
- Thrombosis / thrombectomy
- Angioplasty or stenting
- Access-related infection

- Pseudo-aneurysm or true aneurysm (conduit lumen diameter >9 mm) formation
- Study conduit spontaneous rupture
 - Iatrogenic injuries are not an Event of Special Interest and should be reported as an AE
- Revision or ligation of the study conduit
- Study conduit removal
- Steal syndrome

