#### 2.2.0.2 ***Other Secondary Efficacy Endpoints***

- Rate of interventions required to achieve/maintain Secondary Patency
- Time to loss of Primary Assisted Patency from implantation. Primary Assisted Patency is defined as ‘the interval from the time of access placement until access thrombosis or the time of measurement of patency, including intervening manipulations (surgical or endovascular interventions) designed to maintain the functionality of patent access’ i.e., patent without an intervention to clear a thrombus ([Sidawy 2002](#))
- Histopathological remodeling of any study conduit (based on samples collected)
- The efficiency of dialysis as assessed by spKt/Vurea (obtained from dialysis unit for a subset of subjects)

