## 4.2 ANALYSIS SETS

The primary analysis will be based on the Intent-to-Treat (ITT) analysis set defined as all randomized subjects (based on study conduit group assignment).

The following rules will apply to the ITT analysis set:

- Subjects in whom the wrong conduit is implanted (e.g. an HAV implanted in a subject randomized to an ePTFE graft) will be analyzed within their randomized group rather than in their implanted group
- Subjects in whom no study conduit was implanted will be considered as if abandoned on Day 0 and included in their randomized group
- Subjects in whom the site (upper vs forearm) of implantation is different from the intended site will be analyzed based on the intended site.

The analysis will be repeated using the modified Intent-to-Treat (mITT) analysis set defined as all subjects in whom a study conduit has been implanted (based on actual conduit implanted and the actual site).

A secondary analysis will be conducted in a Per Protocol (PP) analysis set defined as all subjects in whom a study conduit has been implanted (based on actual conduit implanted) and in whom there were no major protocol deviations or data integrity concerns.

Major protocol deviations will be reviewed and verified at the time of determination, the time between the database soft lock and hard lock. Humacyte will identify major protocol deviation categories prior to the close of the database for the primary, second and final analysis. An overall major protocol deviation listing will be reviewed just prior to database lock for final analysis. Humacyte will approve all final major protocol deviation determinations. The protocol deviations SAS dataset will then be generated but will not be entered into the database.

Safety analysis will be conducted using the safety analysis set, which is defined as all subjects who receive study treatment, with the subject's treatment group based on the treatment that was received.

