## 6 EFFICACY ANALYSIS

### 6.1 PRIMARY EFFICACY ENDPOINT AND ANALYSIS

The primary efficacy endpoint is the time to loss of Secondary Patency assessed when all patients are at least 18 months after implantation (or have been censored). The primary analysis will be non-inferiority analysis using the following censoring rules:

- Subjects who have patent study conduits at the time of death, kidney transplant, voluntary withdrawal will be censored at that timepoint
- Subjects who are lost to follow-up will be censored at their last visit when it was known that the study conduit was patent
- Subjects who are lost to follow up and whose study conduit was not patent at the last completed visit will be treated as abandoned at the time of study conduit occlusion
- Subjects in whom a delayed decision is made to abandon the study conduit (e.g. delayed and then failed thrombectomy) will have the date of abandonment set as the date of the initial recognition of the thrombosis, not the date that a final decision is made
- For subjects who discontinue early or who complete without meeting criteria for the event, the time-to-event will be censored and defined as the number of days from randomization to the subject's last visit during the study

These censoring rules will apply to all 'time to' analyses. Subjects with End Stage Renal Disease (ESRD) have significant co-morbidities, with an annual death rate of ~20% (USRDS). Given the nature of the investigational product and the clinical setting, it is unlikely that the investigational product will be a causative factor in the overall death rate, and it is likely that the non-product related death rate will be similar in the two arms. For this reason, the primary analysis of Primary and Secondary Patency will censor deaths. However, a secondary analysis will be conducted in

which death is included as an event in the patency survival curves, to provide re-assurance that death does not modify the outcome of the trial.

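### Read literally, Primary and Primary Assisted Patency have no event for a conduit abandoned, explanted or ligated without a prior qualifying event, and the SAP default rule then censors the subject at the last visit

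*Protocol*

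**What the plan says.** **Events.** Secondary Patency is "the interval from the time of access placement until access abandonment" (Protocol 4.2.1). Primary Patency runs "until any intervention designed to maintain or reestablish patency, access thrombosis or the measurement of patency" (Protocol 4.2.2). Primary Assisted Patency runs "until access thrombosis or the time of measurement of patency" (SAP 2.2.2, Other Secondary Efficacy Endpoints). Neither of the last two names abandonment, removal or ligation.

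**Default censoring.** SAP 6.1 states: "For subjects who discontinue early or who complete without meeting criteria for the event, the time-to-event will be censored", with the time taken to the last study visit. SAP 6.1 applies its censoring rules to every time-to-event analysis. SAP 6.2 repeats this rule directly after naming the Kaplan-Meier estimates for all three patency endpoints.

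**Follow-up.** Protocol 4.1 and 4.3 keep subjects in visits to Month 24 whether or not the conduit is patent.

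**Non-thrombotic loss is foreseen.** Protocol 2.4.3.2 says: "Other factors that may cause graft failure are infections and inappropriate dilatation". Protocol 4.2.3 lists "Revision or ligation of the study conduit", conduit removal, spontaneous rupture, infection and steal syndrome separately from thrombosis.

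**Text pointing the other way.** Both documents gloss Primary Patency as being patent with no interventions. For the ITT set, SAP 4.2 says: "Subjects in whom no study conduit was implanted will be considered as if abandoned on Day 0".

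**The concern.** Take a subject whose conduit is explanted for infection at month 3, with no earlier thrombosis or patency intervention. Secondary Patency is lost at month 3. For Primary and Primary Assisted Patency no listed event has occurred, so the default rule carries the subject event-free to the last visit, which may be Month 24. Patency without intervention would then outlast patency with intervention, which is impossible.

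Primary Patency carries two of the three key secondary confirmatory tests (Protocol 10.3.3; SAP 6.2). Its non-inferiority margin is derived from the observed ePTFE event-free rate, so the rule moves both the estimate and the bound it is judged against. Primary Assisted Patency has its own log-rank test, and there the gap is wider because only thrombosis is a named failure. None of the five sensitivity analyses in SAP 6.3 varies this choice.

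**Working it through.** **1. The plan's own figure.** Protocol 10.5 gives Primary Patency non-inferiority power above 90% (HAV 55% v ePTFE 50% at 6 months) and above 80% (HAV 53%), with N = 350. Assume exponential survival.
- Margin: ln 0.40 / ln 0.50 = 1.322. True hazard ratio: ln 0.55 / ln 0.50 = 0.8625.
- Events with 12 months for everyone: 175 × [(1 − 0.50²) + (1 − 0.55²)] = 253.3.
- Power: Φ(½√253.3 × |ln(0.8625/1.322)| − 1.96) = 92.5%. At 53% it is 83.7%.
- Adding the 16-month accrual gives 96.1% and 89.5%.

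The stated power reproduces. The point disputes no figure in the plan.

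**2. Conduit lost with no earlier thrombosis or patency intervention.**

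| Endpoint | Listed event met? | Written rule that then fits |
|---|---|---|
| Secondary | Yes, abandonment | Event on its date |
| Primary Assisted | No | Censored at last visit |
| Primary | No | Censored at last visit |

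A subject with an earlier thrombosis already has both events. A subject with an earlier patency intervention but no thrombosis has the Primary event only, so the Primary Assisted gap remains.

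**3. Size, scheme A.** The documents give no rate for such losses, so these rates are assumptions. Let h be the intervention or thrombosis hazard: −ln 0.50/0.5 = 1.386 per year for ePTFE and −ln 0.55/0.5 = 1.196 for HAV. Let q be the hazard of loss with no earlier qualifying event. Assume constant hazards, no other censoring, and visits continuing to t = 1.5 years.
- Loss counted as event: exp(−(h+q)t).
- Literal rule: 1 − [h/(h+q)] × [1 − exp(−(h+q)t)].
- ePTFE, q = 0.10: exp(−2.229) = 0.108; literal 1 − 0.9327 × 0.8924 = 0.168.
- HAV, q = 0.03: exp(−1.839) = 0.159; literal 1 − 0.9755 × 0.8410 = 0.180.
- HAV minus ePTFE: +5.1 points with loss as an event, +1.2 under the literal rule.
- ePTFE over q = 0.05 to 0.15: 11.6% to 10.0% with loss as an event; 14.7% to 18.8% literally.

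Scheme A adds q on top of the planning rates, so at q = 0.10 ePTFE patency at 6 months is 47.6%, not 50%.

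**4. Size, scheme B.** Keep 50% at 6 months as the total, and let a share s of first losses be of this type. At 18 months S = 0.50³ = 12.5%. The literal reading is S + s(1 − S). I read the margin as the 10-point rule applied to the ePTFE Primary Patency rate: ln(S − 0.1)/ln S.

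| s (ePTFE) | 18-month ePTFE rate | Hazard ratio margin |
|---|---|---|
| Loss is an event | 12.5% | 1.774 |
| 2% | 14.3% | 1.621 |
| 5% | 16.9% | 1.505 |
| 10% | 21.3% | 1.411 |

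Cox hazard ratio from a simulation with 200,000 per arm, cut at 24 months, true value 0.86:

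| s ePTFE / s HAV | Literal rule |
|---|---|
| 5% / 2% | 0.95 |
| 10% / 4% | 1.02 |
| 10% / 10% | 0.90 |
| 2% / 5% | 0.81 |

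**The case against.** The strongest reply is that the plan never says a lost conduit is censored as patent. Each definition has a further end point, the measurement of patency, and a removed conduit is not patent when measured. The gloss, the patency conditions on censoring at death, transplant and withdrawal, and the Day 0 rule all seem to assume that losing the conduit ends patency. Protocol 2.4.3.2 also says that the final failure is always thrombosis.

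Part of this stands. It would be wrong to say that the endpoints end only at an intervention or thrombosis, or that the plan expressly censors these subjects. That is the result of following the written rules literally, and a sensible programmer might do otherwise.

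The replies do not close the gap:
- Measurement of patency cannot itself be a failure, or every subject would fail at the first check. The SAP wording, which refers to the time of measurement, reads as the end of observation. No rule makes a non-patent finding an event.
- The back-dating rule takes the date of recognised thrombosis, so those subjects already have an event.
- The rule for a non-patent conduit at the last visit covers only subjects lost to follow-up, and dates the loss at occlusion.
- The Day 0 rule assigns abandonment, which neither definition lists.
- The statement that failure is always thrombosis sits beside infection and dilatation in the same list.

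It is also fair that the rates are assumed, and that the Primary Patency tests are confirmatory only after non-inferiority and superiority on Secondary Patency both succeed.

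**Conclusion.** The point holds as a conflict within the text. The definitions and the default rule, taken together, count a conduit lost without a prior qualifying event as event-free after it has gone, while other wording suggests the opposite intent. It bears on two confirmatory tests, their margin and the Primary Assisted Patency test.

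The size is illustrative only. Under scheme A at 0.10 v 0.03 per year, ePTFE 18-month Primary Patency reads 16.8% instead of 10.8%, and the difference between arms shrinks by about 4 points. Under scheme B the margin falls from 1.774 to between 1.621 and 1.411, and a true hazard ratio of 0.86 reads between 0.81 and 1.02. Both schemes assume constant hazards and continued visits after loss.

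A reader might infer three stronger things that the documents do not support:
- **The primary result is compromised.** It is not, because abandonment is the Secondary Patency event.
- **The rule favours the HAV.** The direction depends on which arm loses more conduits this way. If ePTFE has more infection removals, as Protocol 2.5.2 hopes, the rule works against the HAV.
- **An infection benefit is hidden.** Access-related infection is adjudicated and has its own test (Protocol 10.4).

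**What to change.** In Protocol 4.2.2 and SAP 2.2.2, 6.1 and 6.2:
- Define loss of Primary Patency as the earliest of first patency intervention, thrombosis, or abandonment for any reason, including explant, ligation and, in the ITT set, Day 0 non-implantation.
- Define loss of Primary Assisted Patency as the earliest of thrombosis or abandonment for any reason, again including Day 0 non-implantation in the ITT set.
- Use the same abandonment date as for Secondary Patency. Name any abandonment that is censored instead, such as the improved-health rule in SAP 6.1.1, and say which endpoints and analyses it covers.
- Add a derivation check that Primary ≤ Primary Assisted ≤ Secondary patency time for every subject.

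The cost is one sentence per endpoint and a small change to the derivation. Abandonment, removal, ligation and thrombosis are already recorded as Events of Special Interest (Protocol 4.2.3 and 8.3.9), so no new data are needed. In an open-label trial the choice should be in writing before the database lock for the analysis concerned.
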